**Aim 1: Quantify the extent of HA accumulation in shoulder muscles using quantitative MRI and US.**

**(a) T1 $\rho$  MRI:** All images will be acquired using a 3T Prisma whole-body MRI scanner (Siemens Healthcare, Erlangen, Germany) in the Nelson/Harvey building, employing a body coil (Tx)/ flex wrap receive array coil with 8 coil-elements over the pectoralis major and infraspinatus muscles. Anatomical muscle MR images (proton density, T1-w and T2-W) will be acquired using 2D-FSE sequences. A 3D-turbo-FLASH (fast, low angle shot) MRI sequence with a customized T1 $\rho$  preparation module will be used to enable varying spin lock durations (TSL). A paired self-compensated spin-lock pulse will be used to minimize B0 and B1 variations [98]. The sequence parameters will include FOV = 130 mm, matrix size = 256 × 64 × 64, TR = 1500 ms, resolution = 0.5 × 2 × 2 mm^2, spin-lock frequency = 500 Hz, 10 TSL durations = 2, 4, 6, 8, 10, 15, 25, 35, 45, 55 ms. acquisition duration = ~18 minutes for each arm. The MRI body coil will be used for transmission, and vendor supplied flexible receive array coils (8 coil elements each) will be used to image the non-paretic and paretic sides in all subjects. To investigate the extent to which fatty infiltration in skeletal muscle plays a role, Dixon based methods will be used to separate fat and water distribution using the iterative decomposition of water and fat with echo asymmetry and least-squares estimation (IDEAL) technique [99, 100]. The Dixon water/fat imaging parameters will include TR = 9.3 ms, TE = (2.26, 3.08, 3.90) ms, FOV = 180 mm, matrix size = 128 × 128, resolution = 1.4 × 1.4 mm^2, total acquisition time ~ 4.5 min for each arm. Total scan time for both arms will not exceed 90 min.

**MRI Data Processing:** Manual ROIs will be drawn for the pectoralis major and infraspinatus muscles. The mono-exponential T1 $\rho$  mapping will be performed by fitting the signal intensity at different spin-lock durations for each pixel using a three-parameter non-linear mono-exponential model (**Equation 1**) where S is the signal intensity, A is the amplitude, TSL is the spin lock duration, T1 $\rho$  is the mono-exponential relaxation time in the rotating frame, and A0 is the average noise level [22, 23]. For the Dixon water-fat imaging, IDEAL post-processing will be used to separate the water and fat images from the 3-echo images. Water-fractions and fat-fractions will be calculated from the water and fat images. The fat-fraction maps will be used to quantify fat infiltration in the muscles.

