**(b) US Echo Texture Mapping:** Ultrasound imaging will be performed with an Alpinion E-CUBE12R US system (Seoul, South Korea) equipped with an L8-17 transducer with a frequency range of 8 to 17 MHz and a 20-mm width or the Clarius C3 Scanner HD (Vancouver, Canada) in the Motor Recovery Research Lab. The participant will be seated comfortably with the arm supported on an arm rest. The skin surface over the pectoralis major muscle will be marked with the muscle relaxed. All images were acquired with the same US system settings. The musculoskeletal imaging preset will be used with a 10-MHz center frequency, 3-cm depth, and 76-dB dynamic range. The pectoralis major muscle will be visualized in cross section at the location of the skin mark, and images will be acquired with the muscle relaxed, with the US transducer held steadily at the same anatomic location, in a direction perpendicular to the skin surface. Raw RF US data will be saved at a sampling frequency of 40 mega-samples/s.

**US Data Processing:** The intensity of the raw RF US data will be calculated using the Hilbert transform. For each participant, a single B-mode image frame at rest will be selected. Two different types of analyses will be performed. First, we will create spatial parameter maps by estimating the statistical model parameters from the histogram of echo intensities within a moving rectangular window. The window size will be varied from 3 times the acoustic wavelength to 7 times the wavelength. Second, we will select the entire muscle as the ROI for estimating the model parameters. For this analysis, the muscle will be identified manually in the corresponding B-mode images, and the muscle boundary will be manually marked by identifying the hyperechoic fascia boundaries. The entire muscle will be considered the ROI for analysis, including all fascia interfaces inside the muscle boundaries. The backscattered intensities within this muscle ROI will be normalized by the maximum value within the ROI and analyzed as per the theoretical models described in [69].

**US Data Analysis:** The model parameters (signal to noise ratio (SNR), shape and rate of the single gamma distribution, and shape, rate, and mixture probability of the gamma distributions (for example, **Figure 8**) will be estimated from the muscle

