**US Data Processing:** US data acquired from the non-paretic and paretic sides will be processed with a custom program written in Matlab (Natick, MA). Tissue displacements between successive US frames will be estimated from the “raw” US radio frequency (RF) data using cross-correlation techniques [101, 102] with a 1 mm window incremented with a 90% overlap. The term “US frame” refers to the RF data acquired at each time point in the cine-loop. Tissue lateral displacement will be computed for each successive pair of US frames in a  $1 \times 1.5$  cm ROI centered laterally on the midpoint of the image. To visually document the presence of a shear plane within the muscle, we will generate successive displacement maps as a spatial representation of the displacement within the ROI for each pair of US frames. Corresponding cumulative lateral displacement maps will be obtained by summing tissue displacements over time. To calculate the magnitude of shear deformation at a standardized location across subjects, we will use a reference echolucent plane that is relatively stable during the movement and define sub-ROIs each  $2 \text{ mm} \times 10 \text{ mm}$  for analysis. The maximum shear strain in the sub-ROIs will be averaged and used for statistical analysis.

**US Data Analysis:** The mean values and standard deviations of the maximum shear strain will be obtained from the defined regions of interest in the pectoralis major and infraspinatus muscles and will be compared for latent and active PSSP on the paretic and non-paretic sides using mixed model analysis, as described above for Aim 1. We will use Pearson’s correlations to correlate the clinical and imaging measures.

**Expected results, potential pitfalls & solutions:** We expect that the mean maximum shear strain will be statistically significant between the healthy (non-paretic) and paretic latent and active PSSP groups to proceed to the R33 phase. We will have twice as much data for the non-paretic arm than for the latent and active PSSP groups. Since some subjects with stroke may not have perfectly healthy non-paretic sides, we will use the data from the healthiest subjects based on their clinical testing, which may provide a greater separation between these groups. ***The quantitative US data will be collected and analyzed in collaboration with Co-I [name] at Johns Hopkins with Co-I [name] at George Mason University.***

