**c. Statistical plan including sample size justification and interim data analysis.**

We determined our sample size for the R61 Phase based on the more stringent sample size requirement for Aim 2, which will compare two independent groups, i.e., patients with latent PSSP vs. patients with active PSSP in the paretic arm. Because Aims 1 and 2 have different measurements, we present our power analysis in terms of standardized effect sizes (Cohen's d), which would be applicable to either measurement (26).

Langevin et al's data on shear strain mapping in patients with and without low back pain (LBP), showed that the shear strain was reduced in the LBP group ( $56.4\% \pm 3.1\%$ ) compared with the No-LBP group ( $70.2\% \pm 3.6\%$ ), i.e., an extremely large effect size of 3.8, suggesting that large effect sizes are biologically plausible.

The effect sizes in Bishop et al's follow up porcine study (83), showed equally large effect sizes comparing shear strain in control animals versus animals with restricted movement (similar to latent PSSP in our study), versus animals with restricted movement plus injury (similar to active PSSP in our study). We conservatively assume a Cohen's d of 1, which though large is not as large as the cited numbers. To detect a difference between latent PSSP versus active PSSP, a sample size of 17 per group is adequate for statistical significance at the 0.05 level with 80% power. For comparisons between paretic versus non-paretic shoulders, we expect greater power for within-person paired comparisons. However, conservatively assuming no advantage due to within-person correlations, we will also have 80% power to detect differences between latent PSSP versus healthy (non-paretic) shoulders and active PSSP versus healthy shoulders (non-paretic). Since we will be making multiple MRI and US measurements in a population that is disabled and in pain, it is possible that there will be some attrition. Hence accounting for 15% attrition, we will enroll 20 patients per latent PSSP and active PSSP group.

**Figure 10.** Overview of study design for the R61 Phase.

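### No masking to side or pain group is planned for the hand-drawn T1ρ regions (Aim 1) or the discretionary shear-strain reference plane and sub-regions (Aim 2)

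*Combined protocol and SAP*

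**What the plan says.** Aim 1, primary outcome (section 4a, MRI Data Processing and MRI Data Analysis): "Manual ROIs will be drawn for the pectoralis major and infraspinatus muscles". The mean T1ρ relaxation time in each region is then compared between sides and between pain states in a mixed model. The section does not say who draws the regions, what rule fixes their edge, or whether a second reader or repeatability check is used.

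Aim 2, primary outcome (section 4a, US Data Processing under shear strain mapping): displacement is computed by a custom program, and the main region has a fixed size and is centred on the image midpoint. The analysed value is the maximum shear strain averaged over sub-regions of fixed size, placed by reference to "a reference echolucent plane that is relatively stable during the movement". The plan does not say how that plane is chosen, or how many sub-regions there are and where they lie.

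Aim 1, secondary outcome (section 4a, US Echo Texture Mapping): "For each participant, a single B-mode image frame at rest will be selected", and "the muscle boundary will be manually marked by identifying the hyperechoic fascia boundaries".

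Masking: none is described for image acquisition, region placement or analysis. The nearest text is the coding of data in sections 8b and 8d. It serves confidentiality and does not conceal side or pain group.

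Direction: section 2 predicts higher T1ρ in paretic muscle and the lowest shear strain in active pain.

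**The concern.** Each primary value passes through a step that leaves room for judgement, and the person making it may know the arm and the pain group. The protocol gives reason to think that the region edge can matter. Its background describes T1ρ signal as uneven within muscle, and an elbow-pain series in which it lay mainly in the epimysium and outer fascia. The Aim 1 expected results allow for epimysial signal in active pain and perimysial signal in latent pain. Yet the MRI section does not say whether the region includes the epimysium.

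An edge convention applied equally to both arms cancels in the comparison. The risk is differential placement: a slightly wider contour on the paretic side, or a different plane in patients known to have active pain. Because the hypotheses are directional, such a shift would tend to look like the expected result. The Aim 2 expected results tie progress to the R33 phase to significant shear-strain differences, so a false positive would have consequences.

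**Working it through.** **Inputs from section 7c.** Level 0.05 (two-sided assumed, as sidedness is not stated), power 80%, Cohen's d = 1, 15% attrition. The relevant statements are "We conservatively assume a Cohen's d of 1, which though large is not as large as the cited numbers", "a sample size of 17 per group is adequate for statistical significance at the 0.05 level with 80% power", "accounting for 15% attrition, we will enroll 20 patients per latent PSSP and active PSSP group" and, for the side comparison, "conservatively assuming no advantage due to within-person correlations".

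**Inputs assumed.** The documents give no reader bias and no between-side correlation. I take a constant reader shift b of 0.2 or 0.3 SD of a single measurement, and a correlation ρ of 0, 0.5 or 0.7. The value ρ = 0 matches the plan's own conservative case. A paired t test stands in for the planned mixed model.

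**Step 1. Reproduce the plan's sample size.** For two groups of n, the noncentrality is d × √(n/2).
- n = 16, d = 1: 1 × √8 = 2.83, power 78.1%.
- n = 17, d = 1: 1 × √8.5 = 2.92, power 80.7%.

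So 17 per group is correct, and 17 / (1 − 0.15) = 20 enrolled per group.

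**Step 2. Latent versus active, no true difference, reader shift b.** The noncentrality is b × √(17/2), and the two-sided critical t on 32 degrees of freedom is 2.037.
- b = 0.2: noncentrality 0.583, false-positive rate 8.7%.
- b = 0.3: noncentrality 0.875, false-positive rate 13.6%.

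Significance here needs an observed d of about 2.037 × √(2/17) = 0.70, so a shift of 0.2 or 0.3 SD seldom gets there alone.

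**Step 3. Paretic versus non-paretic, no true difference, shift b on the paretic side.** The SD of a within-person difference is √(2(1 − ρ)), so the noncentrality is b × √n / √(2(1 − ρ)). I use 17 pairs (one pain group) and 34 pairs (both groups, 2 × 17). Critical t is 2.120 and 2.035.

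| Pairs | ρ | Noncentrality, b = 0.2 | False positives, b = 0.2 | False positives, b = 0.3 |
|---|---|---|---|---|
| 17 | 0 | 0.58 | 8.5% | 13.0% |
| 17 | 0.5 | 0.82 | 12.1% | 21.4% |
| 17 | 0.7 | 1.06 | 17.0% | 32.4% |
| 34 | 0 | 0.82 | 12.6% | 22.5% |
| 34 | 0.5 | 1.17 | 20.5% | 39.7% |
| 34 | 0.7 | 1.51 | 31.0% | 59.2% |

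With no shift, every entry is 5%. The paired comparison is more exposed because a positive correlation between sides shrinks the SD of the difference, and a constant reader shift does not shrink with it. The same feature that gives the side comparison extra power makes it sensitive to a small systematic error.

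**The case against.** Much of the measurement chain is rule-based. In Aim 2 the displacement is computed, the sizes of the main region and sub-regions are fixed, and the stated purpose is a standardised location across subjects. A reader might infer that both primary outcomes are traced by hand. The documents support that for Aim 1 only; the Aim 2 plane and sub-regions are discretionary, but are not described as manual. The hand-marked ultrasound boundary and the selected frame serve the secondary echo-texture outcome, so they raise the same issue there and not for a primary outcome.

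A reader might also infer that the people who classify patients read the images. No section says who does either, and the plan describes data collection and analysis as collaborations with outside universities. What stands is that no separation of roles is specified.

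Nor is the bias beyond repair. Raw ultrasound data are saved, and where source images are kept a masked reader could redraw regions later. Only bias at acquisition would be unrecoverable.

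Finally, the documents supply no evidence that differential placement would occur, or of its size. That is correct, and it is why the figures above are a sensitivity range and not an estimate.

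**Conclusion.** The gap is real: two primary measurements with room for judgement, directional hypotheses, and no masking to side or pain group. The exposure is greatest in the paired paretic versus non-paretic comparison. Under an assumed 0.2 SD shift and no true effect, the false-positive rate is 8.5–17% with 17 pairs and 13–31% with 34 pairs, for correlations from 0 to 0.7.

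It is tempting to conclude that small reader expectations could produce the latent versus active difference as well. The arithmetic does not support that: the rate there is about 9% at 0.2 SD and 14% at 0.3 SD. The larger percentages belong to the side comparison and depend on the assumed shift and correlation. The sample size of 17 evaluable and 20 enrolled per group is unaffected. This is a cheap improvement, not a flaw that invalidates the design.

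**What to change.** Add to section 4a, for both aims: before any region, reference plane or sub-region is placed, the image files are coded, pain group and side labels are removed, and left-side images are mirrored. The existing image analysts then complete all placements and lock the resulting values, and only after that are the group and side codes merged. The echo-texture frame and boundary steps can follow the same procedure.

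The cost is a file-coding step and a short protocol addition, with no extra patients, visits or readers. Two limits remain: masking to side will be incomplete where muscle atrophy is visible, and the change does not protect against bias while the images are being acquired.

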**Equation 1**

$$S = A \cdot e^{-TSL/T_{1\rho}} + A_0$$

**MRI Data Analysis:** The mean values and standard deviations of T1 $\rho$  relaxation times (ms) will be obtained from the defined regions of interest in the pectoralis major and infraspinatus muscles and will be compared on the paretic and non-paretic sides using mixed model analysis wherein the two sides are nested within one person, and healthy (non-paretic) versus latent PSSP versus active PSSP are examined as fixed effects. Prior to final analysis we will perform model diagnostics to assure that model assumptions regarding the fixed and random effects are met. The mean water and fat fractions of the muscles will also be obtained in percentages to quantify fat infiltration in the muscles, which will be used as predictors in the analysis. We will use Pearson's correlations to correlate the clinical and imaging measures.

**Expected results, potential pitfalls & solutions:** We expect an increase in T1 $\rho$  relaxation times in the paretic pectoralis major and infraspinatus muscles compared with the non-paretic side. We may also see a difference in location of the signal and/or relaxation times between latent and active PSSP. For example, subjects with active PSSP may show higher relaxation times in the

epimysial regions as seen with overuse injury, whereas subjects with latent PSSP may show higher relaxation times in the perimysial region. A two-compartment model of T1ρ mapping (bi-exponential model) can separate out the signal from the GAG content and the free water content of the ECM, and delineate a clearer picture of the extracellular environment of the muscle [23]. We can also analyze the data collected using this model, which may differentiate latent from active PSSP.

[figure not shown]
***All the MRI data will be collected and analyzed in collaboration with co-I [name] at Johns Hopkins in conjunction with [name] at NYU Langone.***

**(b) US Echo Texture Mapping:** Ultrasound imaging will be performed with an Alpinion E-CUBE12R US system (Seoul, South Korea) equipped with an L8-17 transducer with a frequency range of 8 to 17 MHz and a 20-mm width or the Clarius C3 Scanner HD (Vancouver, Canada) in the Motor Recovery Research Lab. The participant will be seated comfortably with the arm supported on an arm rest. The skin surface over the pectoralis major muscle will be marked with the muscle relaxed. All images were acquired with the same US system settings. The musculoskeletal imaging preset will be used with a 10-MHz center frequency, 3-cm depth, and 76-dB dynamic range. The pectoralis major muscle will be visualized in cross section at the location of the skin mark, and images will be acquired with the muscle relaxed, with the US transducer held steadily at the same anatomic location, in a direction perpendicular to the skin surface. Raw RF US data will be saved at a sampling frequency of 40 mega-samples/s.

**US Data Processing:** The intensity of the raw RF US data will be calculated using the Hilbert transform. For each participant, a single B-mode image frame at rest will be selected. Two different types of analyses will be performed. First, we will create spatial parameter maps by estimating the statistical model parameters from the histogram of echo intensities within a moving rectangular window. The window size will be varied from 3 times the acoustic wavelength to 7 times the wavelength. Second, we will select the entire muscle as the ROI for estimating the model parameters. For this analysis, the muscle will be identified manually in the corresponding B-mode images, and the muscle boundary will be manually marked by identifying the hyperechoic fascia boundaries. The entire muscle will be considered the ROI for analysis, including all fascia interfaces inside the muscle boundaries. The backscattered intensities within this muscle ROI will be normalized by the maximum value within the ROI and analyzed as per the theoretical models described in [69].

**US Data Analysis:** The model parameters (signal to noise ratio (SNR), shape and rate of the single gamma distribution, and shape, rate, and mixture probability of the gamma distributions (for example, **Figure 8**) will be estimated from the muscle

images at rest in the non-paretic and paretic pectoralis major and infraspinatus muscles. We will use the SNR parameters to investigate the deviation from purely diffuse scattering. We will then investigate whether the gamma distributions are a good fit to the underlying data using descriptive statistics and the Chi-square goodness-of-fit statistic. The estimated parameters will be compared between the non-paretic and paretic sides. Log transformations will be applied to

**Figure 8.** Histogram of backscattered US intensities in a healthy volunteer and in a patient with cerebral palsy.

[figure not shown]
the rate parameters to approximate normality. Pearson's  $r$  will also be used to assess the correlation between the  $T1\rho$  relaxation times, and the shape and rate parameters of the gamma distributions with sufficiently high signal to noise ratio (SNR) obtained from the statistical echo texture maps US.

**Expected results, potential pitfalls & solutions:** We expect that at least one of the shape and/ or rate parameters for a mixture of two gamma distributions from the backscattered echo intensity of the muscles will correlate strongly with the  $T1\rho$  relaxation times. If so, this will provide a quantitative clinic-friendly tool to infer the GAG/HA accumulation in the muscle, which will enable treatment monitoring. A limitation of using a mixture of gamma distributions is that the quantitative US model parameters cannot directly be linked to some tissue characteristics such as the effective scatterer size or coherent scatterer power, which may be possible with the use of more sophisticated model fits such as the homodyne K distribution. However, the parameters of the gamma distribution do relate to tissue characteristics that affect coherent and diffuse scattering, and changes in the parameters are directly related to changes in the tissue composition and microarchitecture. One advantage of using the mixture of gamma distributions is that the parameter estimation can be performed robustly by using well-established approaches.

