US is more accessible than MRI for clinical imaging [64]. Healthy muscles look dark with sharp bright lines on grey-scale US. The dark signal is hypoechoic and the bright lines represent hyperechoic signal from collagen fibers in the endomysium and perimysium. The echogenicity of muscle tissue can describe alterations in the structure of muscles. Trigger points, which are stiff nodules in a taut band of muscle, present a hypoechoic signal [65, 66], which can be explained by the fact that HA is hydrophilic, and areas of HA accumulation entrain more water and become highly viscous [47, 48]. Increased ECM viscosity leads to “densification” or increased stiffness of the tissue [67]. Qualitative assessment of muscle echo, however, cannot provide an accurate measure of tissue properties [68]. Recently, quantitative US has emerged where the envelope statistics of the radiofrequency components of the backscattered US signal can be used to objectively differentiate tissue properties [69]. US scattering occurs primarily at interfaces, such as connective tissues of the endomysium, perimysium, and fascia and other components, including muscle cells, fat, and fibrous tissue; the mismatch of acoustic impedance can be quantified to provide echo texture maps to characterize tissue properties [70, 71], and statistical maps of muscle echo texture can be used to diagnose myofascial dysfunction [72].

**Thus Aim 1 will quantify the extent of HA accumulation in paretic shoulder muscles compared with the non-paretic side in patients with PSSP using T1ρ MRI, and secondarily correlate the T1ρ MRI measures with US echo texture to develop a clinic-friendly tool to infer extent of HA accumulation.**

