#### 4. Study Procedures

##### a. Study design, including the sequence and timing of study procedures (distinguish research procedures from those that are part of routine care).

All procedures will be conducted solely for study purposes. We will conduct a cross-sectional observational study in 40 patients for the R61 phase. 20 patients will have latent PSSP with non-painful restriction in passive shoulder ER-ROM in their paretic arm, and 20 will have active PSSP with painful ( $\geq 5/10$ ) restriction in passive shoulder ER-ROM as defined above. All 40 subjects will also undergo testing on their non-paretic arm which will serve as a proxy for “healthy” control. All subjects will undergo ***3 types of quantitative imaging of the pectoralis major (key internal rotator) and infraspinatus (key external rotator) muscles of both arms:*** (1) 3-D T1ρ MRI to quantify the extent of HA accumulation (primary outcome for Aim 1), (2) Quantitative US statistical echo texture mapping (secondary outcome for Aim 1), and (3) Quantitative US shear strain mapping to distinguish between latent and active PSSP on the paretic side compared with the non-paretic side (primary outcome for Aim 2).

After obtaining informed consent, subjects will be screened to ensure that they meet inclusion-exclusion criteria. They will then undergo the following clinical and imaging assessments.

**Clinical Assessments:** All clinical assessments will be performed on both arms and be used to correlate with the imaging measures.

Date: August 28, 2023

Principal Investigator: [name]

Application Number: IRB00354876

Passive ROM in the upper limb will be measured at the shoulder (flexion-extension, abduction-adduction, internal and external rotation) in the standard sagittal, horizontal and coronal planes using video and/or 3-D motion capture techniques (Motion Monitor, Innovative Sports Training, Inc., Chicago, IL) [82]. This system uses the trackSTAR 800 sensor (Ascension Technology Corp., VT) that has a static resolution of 0.5 mm for position and 0.1° for angular orientation [83]. During passive ROM, we will also assess muscle stiffness with the Modified Ashworth Scale [84] to determine the degree of resistance [85].

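### A strong correlation with T1ρ is taken to yield a tool for inferring HA and monitoring treatment, but the plan neither reports nor limits the error of the inferred T1ρ

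*Combined protocol and SAP*

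**What the plan says.** The purpose of the echo-texture outcome is given at the end of the MRI/US imaging part of Section 3: T1ρ is to be correlated with echo texture "to develop a clinic-friendly tool to infer extent of HA accumulation". The Innovation section repeats this. Section 7b ranks echo texture as the secondary outcome for Aim 1.

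The only analysis that links the two measures is in Section 4a, Aim 1(b), US Data Analysis: Pearson's r "will also be used to assess the correlation between the" T1ρ relaxation times and the shape and rate parameters of the gamma distributions. The expected-results paragraph that follows says "We expect that at least one of the shape and/ or rate parameters for a mixture of two gamma distributions", fitted to the backscattered intensities, "will correlate strongly with the" T1ρ relaxation times. The next sentence draws the conclusion: "If so, this will provide a quantitative clinic-friendly tool to infer the GAG/HA accumulation in the muscle, which will enable treatment monitoring".

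No value of r, confidence bound or error limit defines a strong correlation. The documents plan no calibration equation, residual error in ms, prediction interval, limits of agreement or repeat reading for this tool.

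On design: "We will conduct a cross-sectional observational study in 40 patients for the R61 phase". On effect size, Section 7c says "We conservatively assume a Cohen's d of 1". It states that standardized effects apply to the Aim 1 and Aim 2 measurements alike, and it carries the same assumption over to the paretic versus non-paretic comparisons.

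**The concern.** Inferring HA accumulation in a patient's muscle from an ultrasound reading is a prediction problem. The useful question is how far the inferred T1ρ may lie from the true one, and whether that error is smaller than the difference the tool has to resolve. A correlation answers a different question, namely whether the two measures move together across the muscles studied. Even a correctly computed r leaves the first question unanswered unless the error is worked out, reported and compared with something.

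Under the plan as written, the study could report a usable individual-level tool when the error for one muscle is larger than the paretic versus non-paretic difference. The correlation would be genuine and the conclusion unsupported.

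The monitoring claim needs further evidence. It requires that change in texture follows change in T1ρ within a person, and a cross-sectional study measures no such change.

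**Working it through.** **Inputs.** Sample size: 40 patients, 20 per group (Section 4a), and 17 per group after the 15% attrition allowed in Section 7c, so 34. Planning difference: Cohen's d = 1 (Section 7c). The SD of T1ρ in ms is not given, because means and SDs in ms are study outputs: "relaxation times (ms) will be obtained from the defined regions of interest in the pectoralis major and infraspinatus muscles". Results are therefore in SD units. The value of r is not given either; 0.7 to 0.8 is an illustrative assumption, shown within a wider range.

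**The plan's own figure.** With d = 1, α = 0.05 (two-sided assumed) and 80% power, a two-sample t test needs 16.7, rounded up to 17 per group (power 80.7%). Then 17 / 0.85 = 20. The stated 17 and 20 reproduce and are not in dispute. They are sized for a group comparison, not for this correlation.

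**Prediction error implied by r.** For a linear fit of T1ρ on one texture parameter:

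- residual SD = √(1 − r²) × SD of T1ρ
- large-sample 95% half-width = 1.96 × √(1 − r²) × SD of T1ρ

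Here SD means the SD across all muscles entering the correlation.

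| r | Residual SD | 95% half-width (SD) |
|---|---|---|
| 0.5 | 0.87 | 1.70 |
| 0.6 | 0.80 | 1.57 |
| 0.7 | 0.71 | 1.40 |
| 0.8 | 0.60 | 1.18 |
| 0.9 | 0.44 | 0.85 |
| 0.95 | 0.31 | 0.61 |

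**Value of r needed for a half-width of 1 SD.** Setting 1.96 × √(1 − r²) = 1 gives r = √(1 − (1/1.96)²) = 0.86.

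**If both sides are pooled.** Cohen's d is in within-group SDs, whereas the table is in SDs of all muscles correlated. If equal numbers of paretic and non-paretic muscles are pooled and differ by 1 within-group SD, the total SD is √(1 + 1/4) = 1.118 within-group SDs. The half-widths become 1.40 × 1.118 = 1.56 at r = 0.7 and 1.176 × 1.118 = 1.31 at r = 0.8. Break-even is at √(1 − r²) = 1 / (1.96 × 1.118) = 0.456, so r is about 0.89.

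**Finite sample.** With N independent pairs, at the mean of the predictor, the half-width is t(0.975, N−2) × √[(1 − r²) × (N−1)/(N−2) × (1 + 1/N)]. For r = 0.7 and 0.8 this gives 1.48 and 1.25 SD at N = 40, and 1.50 and 1.26 SD at N = 34.

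**Uncertainty in r.** Assuming one independent pair per patient, N = 34 and observed r = 0.7, the Fisher-z 95% interval is tanh(0.867 ± 1.96/√31) = 0.47 to 0.84. The matching half-widths are 1.73 and 1.07 SD.

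**The case against.** The strongest reply is that no decision hangs on this sentence. It stands under expected results, concerns a secondary outcome, and belongs to a phase meant to identify and develop measures. The only stated condition for moving to the R33 phase concerns shear strain (Section 4a, Aim 2, expected results). This stands. A reader might infer that the plan contains a formal acceptance rule for the tool, and the documents do not support that. The sentence is still the only statement of what would justify the tool claim, and it runs straight from correlation to tool.

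A reader might also infer that r says nothing about prediction error. That goes too far. Together with the SD of T1ρ across the muscles correlated, r fixes the residual error, and the plan will produce SDs in ms. What is missing is the reporting of that error and a limit on it.

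Nor do the documents show that the tool will fail. They give no value of r, and at r = 0.9 the half-width falls to 0.85 SD of the muscles correlated. The Fisher interval above assumes one pair per patient, whereas the plan measures two arms and two muscles, so it is not the interval of the planned analysis.

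Intended use may also be side-to-side comparison within a patient, not a single absolute reading. The error of such a difference depends on within-person correlation and could be smaller or larger. This limits how literally the figures should be taken, but the plan does not report that error either.

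Finally, before-and-after assessment is placed in the later trial (Innovation section; Figure 9 legend). So the monitoring point concerns wording only, but the wording does present monitoring as following from the correlation.

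**Conclusion.** The concern holds as a gap between the planned analysis and the claim attached to it. The plan infers an individual-level tool and treatment monitoring from a correlation of unspecified strength, with no prediction error reported or limited, and from data containing no change over time.

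At an assumed r of 0.7 to 0.8, the 95% half-width for one muscle is about 1.4 to 1.2 SD of T1ρ, against the plan's own 1 SD planning difference. It falls below that difference only once r exceeds about 0.86, or about 0.89 with pooled sides that differ by 1 within-group SD. These figures rest on a linear relation, normal residuals of constant spread, large-sample limits, and the use of d = 1 as the yardstick for T1ρ. A weaker correlation would still support a statement of association. Because this is an expected-results statement for a secondary outcome, the change is advisable but does not affect the study's primary conclusions.

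**What to change.** In Section 4a, Aim 1(b), US Data Analysis, keep Pearson's r and add:

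- **Regression and validation.** Regress T1ρ on the texture parameter and obtain leave-one-person-out predictions. Leave out all arms and muscles of a person together, and repeat any parameter selection inside each fold.
- **Reporting.** Give the residual SD and the 95% prediction half-width in ms, beside the observed paretic versus non-paretic T1ρ difference with its confidence interval.
- **Wording of the claim.** Describe the result as a tool to infer T1ρ in an individual muscle only if the 95% half-width is smaller than that difference. Otherwise report an association. The rule must name the half-width. Against a 1 SD difference in the same units, the residual SD passes for any r above 0 (above about 0.45 with the pooled SD of 1.118), so a rule based on it would be nearly empty.

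In the expected-results paragraph, reword the monitoring statement as a hypothesis for the later trial.

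The cost is a little analysis code and some wording, with no new patients, visits or measurements. The downside is that the tool claim becomes harder to make. The observed side difference used as the yardstick has its own sampling error, which is why its confidence interval should be shown with it.
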